### 4.3.2 Premature Patient Withdrawal from Study Treatment

Patients may be withdrawn from study treatment for the following reasons:

- Occurrence of a condition or disease that interferes with the study treatment or represents an exclusion criterion.
- Administration of IVIG other than Panzyga. All patients who received at least one dose of the study treatment should be followed up per protocol until the study end without administration of the study product.

- Occurrence of an AE or SAE, which in the opinion of the investigator, precludes further treatment with study medication (Section 7.3.2).

If a patient shows worsening of their symptoms based on CGI-Improvement ratings, they will be presented to the site PI for review and treatment planning. Patients for whom worsening continues at a minimal level ("5" or "mildly worse") for an extended period of six weeks (2 visits) or moderately or greater level ("6" or "7"; much worse or very much worse) since last visit (up to three weeks) will be considered for premature withdrawal from the study drug and administration of appropriate standard of care treatment unless clinical interventions using approved study procedures and/or mediations have a reasonable likelihood to improve symptoms. Patients who experience an emergency worsening of symptoms may at the discretion of the site clinician be withdrawn from the study drug at any time to obtain necessary standard of care treatment. In addition, patients who develop exclusionary criteria (e.g. bipolar disorder, suicide attempt) will be withdrawn from the study drug and will receive appropriate standard of care treatment. All patients withdrawn from the study drug prematurely will be asked to continue the study as planned with modification of the study schedule (e.g. IMP administration and related to it safety lab tests will be omitted). Details of concomitant medications and procedures administrated per standard of care will be captured in patient case reports.

The eCRF will contain an End of Treatment and an End of Study page. The End of Treatment page will record whether the patient will be followed up per protocol, to allow for correct patient status tracking and to provide the reason for the drug withdrawal.

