3.2.2. Secondary Target Variables

Efficacy:

CY-BOCS score at the end of the follow-up period at Week 18 will be compared to the Week 9 scores within the (Panzyga – Placebo) treatment group to assess the durability of the clinical benefit associated with Panzyga treatment.

The protocol specifies the following standardized instruments for the assessment of behavioral changes as secondary efficacy endpoints:

- Clinical Global Impression (CGI) – For the confirmatory endpoint analysis the CGI-I (CGI – Improvement) total score will be used
- Parent & Child OC Impact Scale – Revised (COIS-RP and COIS-RC) – For the confirmatory endpoint analysis the COIS-RP total score will be used
- The Swanson, Nolan, and Pelham Rating Scale (SNAP-IV, 26 item)
- Parent Tic Questionnaire (PTQ)

These scores are therefore considered as secondary target variables; please refer to the protocol for details on these instruments.

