It is important to keep in mind that the primary efficacy evaluation of this study will be based on changes in the total CY-BOCS score from Baseline to Week 9, no data collected in the cross-over phase will be considered. Patients dropping out after Week 9 are not considered as withdrawals for the primary objective of the study.

As the first secondary endpoint is to assess the durability of the clinical benefit, this analysis will be based on data collected throughout the whole study on patients receiving Panzyga in the initial, parallel-group phase (baseline to Week 9) of the study, i.e. on patients randomized to treatment sequence Panzyga – Placebo.

Analyses of all subsequent secondary endpoints will be based on data collected during the parallel-group phase of the study only, i.e. up to Week 9.

After █ patients have completed blinded treatment (Visit Week 9), an interim review of the preliminary safety and efficacy data will be conducted by Independent Data Monitoring Committee (IDMC). At this timepoint, the IDMC will independently evaluate all data accrued in this pivotal study to provide a statement on whether emerging data confirm the prospect of direct benefit and positive risk-benefit ratio for PANS patients treated with Panzyga. IDMC confirmation will justify the submission to concerned Health Authorities of additional study protocol(s) evaluating other dose regimens of Panzyga treatment in patients with PANS. The actual numeric results will not be shared with the Sponsor or Investigators to ensure that bias will not affect subsequent study decisions since the data of the first █ patients will be included in the final statistical analysis.

An interim analysis will be performed by an independent statistician after █ patients have completed the initial 9-week treatment period, to verify the initial assumptions, and to allow for the following adaptations in study design:

1. Adaptive enrichment in the study population

The CY-BOCS scores at Visit 9 will be analyzed with respect to the following covariates/sub-groups in order to identify those that exhibit a promising treatment effect. It will then be determined whether future enrollment will be restricted to any (or a combination) of these:

██████████	██████████	██████████
██████████	██████████	██████████
██████████	██████████	██████████
██████████	██████████	██████████
██████████	██████████	██████████

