All protocol deviations documented during the conduct of the study or identified at the data review process prior to DB lock will be reviewed and classified as minor or major, and with respect to their importance for the planned analyses. This classification of protocol deviations is the joint responsibility of the clinical study manager, the study statistician, and Octapharma's responsible medical expert, and will be agreed and documented before the database is locked or unblinded.

For this study no separate safety population is defined as the FAS coincides with all patients who received at least part of one infusion of Panzyga or placebo. All safety data will thus be analyzed using the FAS. In the event that a patient takes the wrong study drug (i.e., did not take the randomized study drug), the actual treatment received will be used for safety analyses.

All efficacy analyses will primarily be based on the ITT population. In addition, analyses of the primary and secondary endpoints will be repeated on basis of the FAS, unless FAS and ITT coincide. All efficacy analyses will follow the intent-to-treat principle, i.e. patients will be analyzed according to the group they were originally assigned, regardless of what treatment they actually received.

Selected efficacy analyses, but at least the primary and secondary efficacy analyses, will be repeated for the PP population.

Screening failures will only be accounted for in the overall patient disposition, and individual data will be listed.

The assignment of each patient into the respective analysis populations will be determined before the statistical analysis in a data review meeting by a panel consisting of a medical expert from the sponsor, the clinical project manager, the data manager and the study statistician.

8. General Issues for Statistical Analysis

The primary target variable in this study is the CY-BOCS, the mean changes in the total CY-BOCS from Baseline to Week 9 will be compared between Panzyga and Placebo by a confirmatory statistical test to demonstrate superiority.

Descriptive summaries will be presented for each of the primary, secondary, and exploratory variables. In general, summaries will be presented by treatment group in a side-by-side fashion, using a set of standard summary statistics according to the different types of data:

Binary data (whether or not an event has occurred): counts and proportions

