8.2. Withdrawals

All patients enrolled in the trial will be accounted for, and withdrawals will be listed in full detail, including the reasons for withdrawal. Patients who withdraw from the study prematurely will be considered in all data presentations for which they contribute data in the ITT analysis populations.

All patients of the ITT will be included in the primary efficacy analysis, according to the intent-to-treat principle. Patients with missing data, including withdrawals, will be included in the analysis of the primary endpoint by means of the multiple imputation method assuming missing at random (MAR).

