8.3. Handling of Missing Data

For the primary efficacy analysis, missing CY-BOCS results at Week 9 will be subjected to the multiple imputation method assuming missing at random, to include all randomized patients into the analysis.

In an additional sensitivity analysis such missing primary endpoint data will be replaced with the median change observed in the placebo group.

In case of missing weight measurements the last available body weight will be used for calculations related to dosing. In individual patient data listings missing data will however not be replaced by imputed values.

Missing data in secondary analysis variables will not be replaced by any method of imputation; instead, the frequency of missing values will be presented.

For adverse events the following will be applied:

AEs will be reported from the moment that informed consent has been given throughout the complete observation period; AEs with onset after start of the first IMP administration will be considered to be 'treatment-emergent' with respect to the treatment group of the patient at time of onset as defined in section 8.4 below.

If the start date and time of an AE are partially or completely missing, the AE will be considered as treatment-emergent in the analysis if it cannot be definitely shown that the AE did not occur or worsen after first IMP administration (worst case approach). Missing dates and times will not be replaced.

For medications the following will be applied:

A medication will be assumed to be concomitant if it cannot be definitely shown that the medication was not administered after the first IMP administration. Missing dates will not be replaced.

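### SAP 8.3 bars imputation for the confirmatory Week 9 CGI-I and COIS-RP analyses and only counts their missing values, while the primary endpoint gets MAR multiple imputation and a sensitivity analysis

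*SAP*

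**What the plan says.** **Primary endpoint.** SAP 8.3 states that "missing CY-BOCS results at Week 9 will be subjected to the multiple imputation method assuming missing at random", so that every randomized patient enters the analysis. A sensitivity analysis replaces missing values with the placebo group's median change.

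**Secondary variables.** The same section states: "Missing data in secondary analysis variables will not be replaced by any method of imputation; instead, the frequency of missing values will be presented". The readable text makes no exception.

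**Status of the two endpoints.** SAP 3.2.2 makes both confirmatory: "For the confirmatory endpoint analysis the CGI-I (CGI – Improvement) total score will be used" and "For the confirmatory endpoint analysis the COIS-RP total score will be used". SAP 4.1 adds that their analyses "will be based on data collected during the parallel-group phase of the study only, i.e. up to Week 9".

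**Population.** SAP 7 (Analysis Populations) states: "All efficacy analyses will primarily be based on the ITT population". SAP 8.2 guarantees that all ITT patients are included only for the primary analysis. More generally it says: "Patients who withdraw from the study prematurely will be considered in all data presentations for which they contribute data in the ITT analysis populations".

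**Loss to follow-up.** The protocol outline allows for 10% dropout. Protocol 4.3.2 begins: "If a patient shows worsening of their symptoms based on CGI-Improvement ratings, they will be presented to the site PI". It then provides for possible withdrawal from study drug, with the patient invited to stay in follow-up without infusions. Protocol 3.3.1 instead discontinues patients with marked clinical deterioration from the study, with a termination visit.

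**The concern.** The three analyses are all called confirmatory and share the ITT population, yet only one has a readable method for keeping every randomized patient in the test. Read at face value, the rule for CGI-I and COIS-RP leads to a Week 9 comparison of patients who happen to have a Week 9 rating. No reason is given for the difference.

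This matters if loss is related to outcome. CGI-I is both one of the endpoints and the rating that prompts clinical review of a worsening patient. If deterioration takes patients out of the study, and placebo patients deteriorate more often, the remaining placebo group looks better than the randomized one and the estimated difference shrinks. The evaluations that SAP 4.1 schedules every three weeks are the information that could correct this, and a Week 9 observed-case analysis ignores them.

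**Working it through.** **No planned figure to reproduce.** Sample size, effect size and SD are redacted. The readable values are 80% power, 2.5% type I error, 10% dropout and 1:1 allocation, and these do not fix a sample size. The check is therefore an illustrative simulation.

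**Assumptions (none from the documents).** Normally distributed scores at Weeks 3, 6 and 9; 50 patients per arm; correlation between visits of 0.5 or 0.7; a Week 9 effect of 0 or 0.5 SD, with one third of it present at Week 3 and two thirds at Week 6. The Week 9 score is missing when the Week 3 or Week 6 score exceeds a worsening threshold. The threshold is the same in both arms and set to give 5%, 10% or 20% missing overall. There were 4,000 runs per setting, with a one-sided test at 0.025.

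**Estimators.** (a) Full data. (b) Week 9 observed cases, t-test. (c) A MAR estimate that predicts missing Week 9 scores from treatment and the Week 3 and Week 6 scores.

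**Results, true effect 0.5 SD.** Attenuation = 1 − (observed-case estimate ÷ full-data estimate).

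| Missing | Correlation | Full | Observed-case | MAR | Attenuation |
|---|---|---|---|---|---|
| 5% | 0.5 | 0.505 | 0.479 | 0.504 | 5.1% |
| 5% | 0.7 | 0.504 | 0.468 | 0.503 | 7.1% |
| 10% | 0.5 | 0.503 | 0.462 | 0.503 | 8.2% |
| 10% | 0.7 | 0.501 | 0.445 | 0.500 | 11.2% |
| 20% | 0.5 | 0.497 | 0.439 | 0.498 | 11.7% |
| 20% | 0.7 | 0.496 | 0.418 | 0.496 | 15.7% |

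At 10% overall, about 12% of placebo and 8% of active patients are missing. This imbalance comes from the treatment effect alone, because the rule is identical in both arms.

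**Type I error, no effect.** Observed-case rejection was 0.023 to 0.031, against 0.022 to 0.031 on full data. The simulation standard error is √(0.025 × 0.975 ÷ 4000) ≈ 0.0025. There is no sign of inflation.

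**Power at 10% missing.**
- Loss after worsening: 0.704 to 0.614 (a drop of 0.090, correlation 0.5) and 0.709 to 0.628 (a drop of 0.081, correlation 0.7).
- Purely random 10% loss (correlation 0.7): 0.686 to 0.639 (a drop of 0.047), with no bias (0.496 against 0.497).
- Direct calculation: the noncentrality is 0.5 × √(n/2), which is 2.50 for 50 per arm and 2.37 for 45. Power is 0.697 and 0.650, again a drop of 0.047.
- Share due to smaller numbers: 0.047 ÷ 0.090 = 52% and 0.047 ÷ 0.081 = 58%. So rather more than half of the power loss would occur without any bias.

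**COIS-RP.** The table describes a scale whose own earlier values drive the loss, which fits CGI-I better. Suppose instead that CGI-I drives the loss and COIS-RP correlates with it at 0.3 to 0.7 at the same visit. With a visit correlation of 0.7, the correlation of Week 9 COIS-RP with earlier CGI-I is 0.3 × 0.7 = 0.21 to 0.7 × 0.7 = 0.49. Attenuation at 10% missing is then about 4 to 7%.

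**The case against.** **The models are hidden.** SAP 10.1 and 10.2 and protocol 9.2.2 and 9.2.4 are unreadable. The SAP's version history mentions covariates for multiple imputation that appear nowhere in the readable text, so some missing-data detail does sit behind the redactions. A ban on replacing values also does not exclude a likelihood-based repeated-measures model, which uses Week 3 and Week 6 ratings under MAR without filling anything in. A reader might infer that the plan certainly drops patients without a Week 9 rating; the documents do not establish that. What remains is that the section on missing data names no such model and says that missing values will be counted instead.

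**Worsening may not cause missing ratings.** It is tempting to read the CGI-I rule in protocol 4.3.2 as the source of missing Week 9 data. It is not: that rule is discretionary, stops study drug rather than follow-up, and asks patients to stay on. The study outline says the same. Only protocol 3.3.1 takes deteriorating patients out of the study, and it names no CGI-I trigger. This objection stands against any claim that the withdrawal rule itself produces the loss. It does not remove the risk, because the two sections conflict, continuing is by request, and 10% dropout is expected anyway. The Early Termination Visit follows Week 18 procedures, and the readable text does not say that its rating stands in for Week 9.

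**MAR is not guaranteed either.** Emergency withdrawal at a clinician's discretion could reflect changes between visits that no scheduled rating records. If that led to missing ratings, MAR methods would not remove all bias. This is a reason for a sensitivity analysis.

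**Conclusion.** The point holds in a limited form. The readable SAP gives two confirmatory ITT analyses neither a MAR-based method nor a sensitivity analysis, although it gives the primary endpoint both. If SAP 10.2 does not supply a repeated-measures model, randomized patients without a Week 9 rating fall out of these tests. To the extent that loss follows earlier worsening, the observed-case estimate can be biased, probably toward no difference.

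At the planned 10% dropout the illustrative attenuation is about 8 to 11%, and less for COIS-RP if CGI-I drives the loss. That figure assumes that all of the loss follows worsening, and it rests on an assumed effect, correlation, sample size and normal scores. Loss for unrelated reasons would cost power without bias.

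A reader might go further and infer that the tests risk false positives. The check does not support this: type I error was intact under a common dropout rule, and inflation would need rules that differ by arm, which the documents do not show. Nor do they show loss driven by adverse events that would exaggerate the benefit.

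**What to change.** 1. **SAP 8.3.** For Week 9 CGI-I and COIS-RP, replace the ban with MAR multiple imputation or an MMRM. Use treatment, the stratification factors (antibiotic prophylaxis, PANS/PANDAS, stable SSRI use), the available earlier post-baseline ratings of the same scale, and a baseline covariate. CGI-I is itself rated relative to baseline and has no baseline value, so use baseline CGI-S for it; use baseline COIS-RP for COIS-RP. The COIS-RP visit schedule is not readable, so confirm which earlier ratings exist.
2. **Sensitivity.** Add one sensitivity analysis per endpoint, parallel to the primary endpoint's. For CGI-I the analogue of the placebo median change is the placebo median rating. Keep observed-case analysis as supportive.
3. **If SAP 10.2 already specifies such a model,** a cross-reference in SAP 8.3 and the sensitivity analysis are enough.
4. **Protocol.** Sections 3.3.1 and 4.3.2 must be reconciled on whether deteriorating patients leave the study or only the study drug. Which rule is right is a clinical matter and is not addressed here.

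The cost is a short SAP edit, some additional programming alongside the imputation already planned for the primary endpoint, and reliance on the MAR assumption. No new data are needed.

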8.4. Derived and Computed Variables

The following derived/computed variables have been initially identified as important for the analysis of the primary and secondary target variables. It is expected that additional variables and flags will be required. The SAP will not be amended for additional variables that are not related to the primary target or key secondary target variables. Any additional derived or computed variables will be identified and documented in the SAS programs that create the analysis files. If the SAP is not amended, further derivations related to primary and secondary target variables will be described in the CSR.

- The age of a patient is defined according to the usual definition that a person is n years old until she or he has completed her or his (n+1)th year of life, using the date of informed consent as the reference date. This is also the definition that will be applied for evaluation of the age related inclusion criteria. [Unit: years]
- Body Mass Index: $BMI = (\text{Body weight}) / \text{Height}^2$ [Unit: kg/m^2]
- Treatment group for safety analyses: Because of the cross-over follow-up phase in this study, safety data will be summarized in 3 groups:
 1. 'Panzyga': Patients with either
 - Panzyga as the first IMP administered, from start of treatment and up to 21 days after the end of the last Panzyga infusion, or with
 - Panzyga as their 2nd treatment, from start of Panzyga treatment until the end of the observation period.
 2. 'Placebo': Patients with Placebo as their first IMP administered, from start of treatment until the first administration of Panzyga.
 3. 'Placebo after Panzyga': Patients who received Panzyga in the first period and are now treated with Placebo, from 22 days after the last Panzyga administration until the end of the observation period.

Derivations with respect to evaluation/scoring of the standardized assessment tools/questionnaires used in this study (CY-BOCS, CGI, COIS, SNAP-IV, PTQ, C-SSRS) will be done according to the respective scoring manuals and are therefore not detailed in this SAP.

Property of Octapharma. Do not copy or distribute without written permission.

9. Study Patients and Demographics

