During the first phase of the study (i.e. three infusion cycles), patients will repeat the behavioral and laboratory parameter assessments performed at Baseline and the primary endpoint will be evaluated at Week 9 Visit. Data for evaluation of secondary endpoints will also be collected. Thereafter, crossover treatment assignment will occur in a blinded fashion for the second phase of the study. In the second phase of the study (Week 9, 12, 15, and 18 visits), patients who received Panzyga in the first phase will be assigned placebo and vice versa. During this second phase, three infusion cycles of either Panzyga (1 g/kg BW daily for two consecutive days) or placebo (0.9% w/v sodium chloride infusion equivalent in volume to 1 g/kg BW Panzyga daily for two consecutive days) will be given at three-week intervals at the study site. The patients' conditions will be monitored throughout the infusion session. Upon completion of the second phase of the study, at the Week 18 Visit, data for evaluation of secondary endpoints, including durability of the clinical benefit and safety data, will be collected.

If a patient shows worsening of their symptoms based on CGI-Improvement ratings they will be presented to the site PI for review and treatment planning. Patients for whom worsening continues at a minimal level ("5" or "mildly worse") for an extended period of six weeks (2 visits) or moderately or greater level ("6" or "7"; much worse or very much worse) since last visit (up to three weeks) will be considered for premature withdrawal from the study drug and administration of appropriate standard of care treatment unless clinical interventions using approved study procedures and/or medications have a reasonable likelihood to improve symptoms. Patients who experience an emergency worsening of symptoms may at the discretion of the site clinician be withdrawn from the study drug at any time to obtain necessary standard of care treatment. In addition, patients who develop exclusionary criteria (e.g. bipolar disorder, suicide attempt) will be withdrawn from the study drug and will receive appropriate standard of care treatment. All patients withdrawn from the study drug prematurely will be asked to continue the study as planned with modification of the study schedule (e.g. IMP administration and related to it safety lab tests will be omitted). Details of concomitant medications and procedures administrated per standard of care will be captured in patient case reports.

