### **8.6.2 Independent Data Monitoring Committee**

An IDMC will be established by the Sponsor. The IDMC will be composed of recognized experts in the fields of pediatric immunology, neurology, psychiatry and statistics, respectively, who are not actively recruiting patients. Enrollment was discontinued after the first six patients had been enrolled in order to enable a planned IDMC review of unblinded safety and PK data. Enrollment resumed only after the IDMC data review of these first six patients had been completed at Week 6 (Cycle 3), and the IDMC had recommended to continue enrollment into the study. Thereafter, IDMC meetings will be scheduled on a quarterly basis.

The IDMC will review relevant data periodically during the study and will give advice on the continuation, modification, or termination of the study. A written study-specific procedure will define in detail the composition, responsibilities, and procedures of the IDMC.

The IDMC will have the following responsibilities:

- to review relevant safety data periodically;
- to review TEEs and HTRs in a timely fashion;
- to give advice on the continuation, modification, or termination of the study.

A Charter will be prepared before study start and will define in detail the composition, responsibilities, and procedures of the IDMC.

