4.1. Overall Study Design and Plan

Study NGAM-13 is designed as a prospective, multicenter, randomized, double-blind, parallel group, placebo-controlled, phase 3 superiority study, with an additional double-blind, crossover safety and efficacy follow-up phase.

In the first phase of the study, from enrolment to Week 9, patients will receive Panzyga or placebo administered 3 times within 9 weeks in 3-week intervals, according to their randomized treatment sequence. After Week 9 all patients will be switched to the alternative for another 3 treatments in the crossover phase of the study. Dosing and dosing intervals will be the same for all study drug administrations in both study phases, namely Panzyga 2 g/kg bodyweight (BW), administered as 1 g/kg BW daily for two consecutive days) or placebo (0.9% w/v sodium chloride infusion equivalent in volume to 1 g/kg BW Panzyga daily for two consecutive days).

Up to █ sites (USA and rest of the world) are projected to participate.

After the first █ patients have been enrolled, the study enrollment will be put on hold until the Independent Data Monitoring Committee (IDMC) has reviewed unblinded safety and PK data of these █ patients and given the green light to pursue the study.

The duration of the initial parallel-group phase will be 9 weeks, plus up to 28 days from screening to randomization, the duration of 2nd phase after the crossover will also be 9 weeks. After the initial phase patients will directly continue with the second phase without any wash-out time.

Patients eligible after screening will be randomized in a balanced 1:1 ratio to one of two treatment sequences:

- (Panzyga – Placebo): 3 administration cycles with Panzyga, followed by 3 administration cycles with placebo
- (Placebo – Panzyga): 3 administration cycles with placebo, followed by 3 administration cycles with Panzyga

The study population will be prospectively balanced according to the stratification factors specified in section 3.2.4 above. Psychological and behavioral evaluations, in particular the CY-BOCS, will be conducted at every visit, i.e. every 3 weeks during the initial parallel-group phase and at Week 18 / Final Visit; please refer to the protocol for the complete flow chart of assessments.

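### The 21-day Panzyga window in SAP 8.4 covers both infusion days of the first placebo cycle on the nominal schedule, so some infusional AEs of saline infusions are tabulated under 'Panzyga'

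*SAP*

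**What the plan says.** SAP 8.4 defines three groups for the safety tables.

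- 'Panzyga', for patients who start on it: "Panzyga as the first IMP administered, from start of treatment and up to 21 days after the end of the last Panzyga infusion". Patients who cross over to it are also counted here: "Panzyga as their 2nd treatment, from start of Panzyga treatment until the end of the observation period".
- 'Placebo', for placebo-first patients until their first Panzyga infusion.
- 'Placebo after Panzyga', which begins "from 22 days after the last Panzyga administration until the end of the observation period".

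SAP 8.3 assigns treatment-emergent AEs "with respect to the treatment group of the patient at time of onset as defined in section 8.4 below". SAP 11 applies the same three groups to the safety tabulations. SAP 11.1 makes them the usual columns of the AE tables and lists infusional AEs at 1, 24 and 72 hours among the key figures. SAP 11.4 does something different for vital signs: it summarizes them by the product actually given at each infusion.

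On timing, SAP 4.1 states: "After the initial phase patients will directly continue with the second phase without any wash-out time".

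**The concern.** A carry-over window is a reasonable convention for AEs in general, because an effect of Panzyga can appear after the last dose. It does not suit infusional AEs. SAP 11.1 defines these only by time from an infusion and sets causality aside, so the table describes how the infused product was tolerated. If the window reaches into the first placebo cycle, events that belong to a saline infusion by that definition are shown as Panzyga events.

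Two inconsistencies follow. Vital signs and infusional AEs from the same saline infusion can appear in different columns. The 72-hour period after one saline infusion can also be split between two columns.

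**Working it through.** The SAP states no figure to reproduce here. The check is a day count, followed by a count of infusions.

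**Inputs**

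- Each cycle is two consecutive infusion days, with three cycles per phase at three-week intervals (Protocol 5.4).
- Cycle 3 is at Week 6. Protocol 8.6.2 refers to the "data review of these first six patients had been completed at Week 6 (Cycle 3").
- The crossover starts at Week 9. The Study Procedures text of the Protocol outline begins "In the second phase of the study (Week 9, 12, 15, and 18 visits"), and SAP 4.1 rules out a wash-out.
- Allocation is 1:1 (SAP 4.1), so one completer per sequence is used for the pooled count.

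**Day count, with Day 0 as the first infusion**

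- Cycle *k* is infused on Days 21(*k* − 1) and 21(*k* − 1) + 1. This gives Days 0/1, 21/22 and 42/43 for the first phase and Days 63/64 for the first crossover cycle.
- In the Panzyga–Placebo sequence the last Panzyga infusion is on Day 43.
- The first two saline infusions come 63 − 43 = 20 days and 64 − 43 = 21 days later.
- The 'Panzyga' window ends on Day 43 + 21 = 64. 'Placebo after Panzyga' starts on Day 43 + 22 = 65.

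Both saline infusion days are inside the 'Panzyga' window.

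**Where the infusional AEs of these two saline infusions go (calendar days)**

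| AE window | 'Panzyga' | 'Placebo after Panzyga' |
|---|---|---|
| During, or within 1 hour | all | none |
| Within 24 hours | onset Days 63–64 | onset Day 65 |
| Within 72 hours | onset Days 63–64 | onset Days 65–67 |

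**Share of infusions, and sensitivity to the timing of the crossover visit**

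A Panzyga–Placebo completer contributes 6 Panzyga infusions to the 'Panzyga' column, plus any saline infusions inside the window. A Placebo–Panzyga completer contributes 6 Panzyga infusions.

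| First crossover cycle | Saline infusions covered | Share of pooled 'Panzyga' column | Saline infusions left in 'Placebo after Panzyga' |
|---|---|---|---|
| One day early | 2 | 2/(6 + 2 + 6) = 2/14 = 14.3% | 4 of 6 |
| On time | 2 | 2/14 = 14.3% | 4 of 6 |
| One day late | 1 | 1/(6 + 1 + 6) = 1/13 = 7.7% | 5 of 6 |
| Two or more days late | 0 | 0/12 | 6 of 6 |

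Within a single Panzyga–Placebo completer the saline share is 2 of 8, 1 of 7 or 0 of 6 for on time, one day late, and two or more days late.

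**Clock-time reading**

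The window then closes on Day 64 at the time of day when the Day 43 infusion ended. The Day 63 saline infusion and the hour after it are still covered. The Day 64 infusion is covered only up to that time.

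As an illustration, assume that the Panzyga infusion ended between 12:00 and 16:00, that saline starts between 08:00 and 10:00, and that it runs 3 to 5 hours. The first saline infusion and the following 21 to 29 hours are then always inside. The second always starts inside, but it ends anywhere from 5 hours before the cut-off to 3 hours after it. A later start on Day 64 could put that infusion wholly outside.

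The 21-day and 22-day limits meet without a gap only in calendar days. In exact time, an onset between 21 and 22 days belongs to neither group.

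**The case against.** The strongest reply is that the window is deliberate. SAP 8.4 introduces the groups because of the crossover, and SAP 11 repeats the 21-day cut and adds a medical review of later events. With three-week cycles and no wash-out, any such window must overlap the first crossover cycle. It counts doubtful events against Panzyga, in line with the worst-case approach to AE dating in SAP 8.3. IgG exposure is also likely to persist at Week 9, so an event during the first saline infusion cannot be attributed cleanly to saline. This holds for the general AE tables, and nothing proposed here changes them. It does not carry over to infusional AEs, whose definition ignores causality. Nor is the direction always conservative: saline events raise the count, but saline infusions in a per-infusion denominator could dilute a rate.

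A second reply is that the plan leaves room for an exception. SAP 11.1 gives its column rule only as a general one, SAP 8.4 allows further derived variables to be documented in the programs, and the table shells are to come in a separate document. The Protocol's safety analysis section (9.2.3) cannot be read in the public version. An exception may therefore exist out of sight. The visible text states none, and an unstated exception leaves the choice to programming.

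It is also fair to say that 14% is a share of infusions and not of events, and that coverage of both days depends on counting in calendar days and on the visit being no later than planned. Those limits stand.

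**Conclusion.** The point holds and is minor. On the nominal schedule, in calendar days, two of the six saline infusions of each Panzyga–Placebo completer fall inside the 'Panzyga' safety window, and part of their infusional AEs goes into that column. By clock time, the first of the two is still covered.

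The result rests on cycle 4 being given at Week 9, on equal numbers of completers per sequence for the pooled share, and on no exemption for infusional AEs in the redacted text. Visit windows are redacted and event rates are not given, so the effect on AE counts cannot be estimated. It is confined to descriptive safety tables. The placebo-first column and all efficacy analyses are unaffected.

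**What to change.** In SAP 11.1, state that infusional AEs at 1, 24 and 72 hours are tabulated by the product actually given at the infusion concerned, following the rule in SAP 11.4. If a rate is shown, use the number of infusions of that product as the denominator. Keep the SAP 8.4 grouping for the general AE tables, with a footnote identifying AEs with onset between the first placebo infusion and the end of the 21-day window.

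The cost is one sentence, one derivation flag and one footnote. No new data should be needed, because the 1-, 24- and 72-hour tables already require onset relative to an infusion and SAP 11.4 already requires the product given at each infusion. The drawback is that one event can appear under different columns in the general and infusional tables. The footnote explains this.
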